### 15.4 Serious Adverse Event and Adverse Event Severity

The Investigator will assess the severity of the AE using the following general guidelines:

- **Mild:** An AE that is usually transient, requiring no special treatment, and does not interfere with the subject’s daily activities.
- **Moderate:** An AE that introduces a low level of inconvenience or concern to the subject and may interfere with daily activities, but is usually ameliorated by simple therapeutic measures.
- **Severe:** An AE that interrupts a subject’s usual daily activity and typically requires systemic drug therapy or other treatment (a severe AE may not necessarily qualify as an SAE).
- **Life-threatening:** An AE that put the subject at immediate risk of death from the event as it occurred. This does not include an event that might have led to death if it had occurred with greater severity.
- **Fatal:** An AE that was the cause of the subject’s death

### 15.5 Adverse Event Outcome

The Investigator will categorize the outcome of each SAE and AE according to the definitions below:

- **Resolved:** The subject recovered from the SAE or AE.
- **Resolved** with sequelae: a condition whereby the consequences of a disease or injury include lingering effects.
- **Ongoing:** At the time of the last assessment, the event is ongoing, with an undetermined outcome. Note: Ongoing SAEs and AEs are not considered resolved as a result of death and no SAE or AE stop date should be recorded for an AE that is ongoing at the time of death.
- **Fatal:** Adverse Event directly caused death. The Sponsor may request that the Investigator perform or arrange for the conduct of supplemental measurements and/or evaluations. If a subject dies during participation in the study or during a recognized follow-up period, the Sponsor should be provided with a copy of any post-mortem findings, including histopathology. Note: Death is an *outcome* of an adverse event and not an adverse event in itself. All reports of subject death should include an adverse event term (other than "Death") for the cause of the death.

Since reporting of an SAE is required within 24 hours of discovery, Death can be reported as an initial event term and updated to the final diagnosis in a follow-up report. If an adverse event term is not provided, the Investigator will be queried to obtain the cause of death. Only in the rare occurrence that no verbatim description of an adverse event can be obtained from the investigative site will "Death – Unknown Cause" be used as the event term.

The Investigator should attempt to establish a diagnosis of the event based on the signs, symptoms and/or other clinical information. In such cases, the diagnosis should be documented as the AE (and SAE if serious) and not the individual signs/symptoms.

In the case of abnormal labs or diagnostic tests judged to be clinically significant by the Investigator a diagnosis, if known, or clinical signs or symptoms if the diagnosis is unknown, rather than the clinically significant laboratory finding or abnormal assessment, should be used to complete the AE or SAE eCRF. If no diagnosis is known and clinical signs or symptoms are not present, then the abnormal finding should be recorded on the AE or SAE eCRF. If an SAE report is completed, pertinent laboratory data should be recorded on the SAE eCRF, preferably with baseline values and copies of laboratory reports.

### 15.6 Prompt Reporting of SAEs to Sponsor

The Sponsor has requirements for reporting serious adverse events to regulatory agencies for a drug under clinical investigation. The Sponsor must be notified **within 24 hours of discovery** if the Investigator determines that an adverse event meets the protocol definition of an SAE.

All SAEs occurring from the time of LevoCept insertion through study exit require immediate reporting to the Sponsor. Investigators should not wait to receive additional information to fully document the event prior to notifying the Sponsor but should provide as much relevant information as immediately available.

Further details of the event can be provided as they become available. The procedures for reporting SAEs are as follows:

- Complete the “Serious Adverse Event Report” form;
- Submit the completed form to Sponsor;
- For fatal or life-threatening events, also submit copies of hospital case reports, autopsy reports, and other documents when requested and applicable;
- The Sponsor may request additional information from the Investigator to ensure the timely completion of accurate safety reports;
- Any fatal or life-threatening events should also be reported immediately by telephone to Sponsor;
- The SAE eCRF should be completed as thoroughly as possible and signed by the Investigator before transmittal to Sponsor. It is very important that the Investigator provides an assessment of the causal relationship between the event and the study device at the time of the initial report; and
- The Investigator, or responsible person according to local requirements, must comply with the applicable local regulatory requirements concerning the reporting of SAEs to regulatory authorities and the IRB.

#### **15.7 Clinical Laboratory Abnormalities and Other Abnormal Assessments as Adverse Events and Serious Adverse Events**

Abnormal laboratory findings (e.g., clinical chemistry, hematology) or other abnormal assessments (e.g., electrocardiogram, X-rays, vital signs) per se are not reported as AEs. However, abnormal findings that are deemed **clinically significant** (i.e., associated with signs and/or symptoms or requiring therapeutic intervention) must be recorded as AEs if they meet the definition of an adverse event (and recorded as an SAE if they meet the criteria of being serious) as described previously. Clinically significant abnormal laboratory or other abnormal findings that are detected after study device placement or that are present at baseline and worsen following the placement of LevoCept are included as AEs (or SAEs if serious).

The Investigator should exercise his or her medical judgment in deciding whether an abnormal laboratory finding or other abnormal assessment is clinically significant. A clinically significant laboratory abnormality in the absence of clinical symptoms may also jeopardize the subject and may require intervention to prevent immediate consequences (e.g., a markedly high serum potassium concentration may not be accompanied by arrhythmia, yet be of a magnitude to require potassium-binding resin administration to prevent such sequelae). Subjects should undergo repeat testing of clinically significant abnormal laboratory findings as soon as they are recognized.

#### **15.8 Documenting Adverse Events**

Any AE occurring from the beginning of the study device placement procedure through Study Exit must be documented in the subject’s study records and on the AE eCRF. SAEs that occur during the study must be documented in the subject’s study record, on the AE eCRF and on the SAE eCRF as appropriate.

The investigator's assessment of causality, severity and status of the adverse event must be documented. When a causality assessment is provided for a serious adverse event, it is important to include a rationale for the assessment so that a better understanding of the reported event can be compiled. The rationale should be accompanied by all available supporting evidence, including relevant laboratory tests, histopathology evaluations and the results of other diagnostic procedures. The Investigator's rationale with supporting evidence is valuable when Sponsor performs a cumulative analysis of similar events.

#### **15.9 Follow-up of Adverse Events and Serious Adverse Events**

All AEs and SAEs must be followed until resolution, the condition stabilizes, 30 days post study device removal, or the subject dies or is lost to follow-up (including withdrawal of consent), whichever occurs first. The Investigator is responsible to ensure that follow-up includes any supplemental investigations as may be indicated to elucidate as completely as practical the nature and/or causality of the AE/SAE. This may include additional laboratory tests or investigations, histopathologic examinations, or consultation with other health care professionals. Follow-up information should be submitted to the Sponsor in a timely many as the information is obtained.

#### **15.10 Clarification in Reporting of Deaths**

All subject deaths (regardless of relationship to study device) should be reported that occur from the beginning of study device placement through Study Exit. The information should be recorded on the Subject Death form and the SAE eCRF.

#### **15.11 Post-Study Treatment Reporting Requirements**

For all enrolled subjects, all AEs and SAEs, regardless of cause or relationship, that occur from the beginning of study device placement through Study Exit require reporting to the Sponsor. In addition, if the Investigator learns of any SAE at any time after a subject has had the study device removed, and such event seems reasonably related to study drug, the Investigator should immediately notify the Sponsor.

#### **15.12 Study Device Malfunction**

Should the study device not perform mechanically as expected, it is essential that it be returned to the study Sponsor for assessment.

### **16. PROTOCOL VIOLATIONS and DEVIATIONS**

Except in the event of a medical emergency or where it is necessary to protect the safety, rights or welfare of the study subject, any changes to the protocol will require written approval of ContraMed LLC or designee. Violations or deviations from the Clinical Investigational Plan to protect the health and safety of the subject will be reported to the IRB and as required by local regulations. All protocol violations or deviations will be recorded, tracked and reviewed periodically by ContraMed and its designee, according to process established prior to first patient enrolled. A protocol violation or deviation may be requested in advance of implementation and will be reviewed for approval by ContraMed or its designee, or a violations/deviation may be identified after the fact, by the Investigator, ContraMed, or the monitoring staff. Investigators will be asked to provide an explanation for the all violations and deviations identified. ContraMed, or designee, will be responsible for analyzing deviations and may implement corrective actions as necessary.

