### **6.3 Minimization of Anticipated Risks**

Potential risks that may be associated with use of LevoCept have been minimized in this study by the following:

- a. Establishing eligibility criteria that exclude subjects who are at higher risk for experiencing an anticipated adverse event;
- b. Conducting extensive preclinical and clinical testing prior to the start of this Phase II clinical study;
- c. Conducting a risk analysis and incorporating mitigations to eliminate and/or reduce risks to as low as possible in accordance with ISO 14971-Medical Devices – Application of risk analysis to medical devices
- d. Selecting investigators with proper level of training and experience in placing IUDs;

---

 Prescribing Information, Mirena, Bayer Healthcare

- e. Ensuring adequate monitoring is performed to identify any safety issues associated with the study procedure and subjects;
- f. Regularly reviewing reported serious adverse events and adverse events throughout the study and taking appropriate medical measures to resolve the adverse events.

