#### **8.1 Inclusion**

Subject must meet all of the following criteria to participate in this study:

1. Between 18-40 years of age at the time of study initiation;
  - 1.1 Enrollment will be targeted for 225 subjects aged 18-35 (for safety and effectiveness analyses) and an additional 25 subjects aged 36-40 (for safety only); (note: all subjects will be included in the analysis for device placement and tolerability);
2. Pre-menopausal, as determined by regular menstrual cycle ( $28 \pm 7$  days) for the last 3 months;
  - 2.1 Based on patient history when not on hormonal contraceptives;
3. Sexually active with a male partner who has not had a vasectomy;
4. Reasonably expect to have coitus at least once monthly during the study period
5. In a mutually monogamous relationship of at least 3-6 months duration
6. Seeking to avoid pregnancy for the next 12 months;
7. Willing to use the study device as the sole form of contraception;
8. Willing to accept a risk of pregnancy;

9. Subjects who are age 21 or older, at time of informed consent, must have a normal PAP or ASC-US with negative high risk HPV test result within the appropriate screen timeframe, and prior to LevoCept insertion;
10. Able and willing to comply with all study tests, procedures, assessment tools and follow-up; and
11. Able and willing to provide and document informed consent and Authorization to Release Protected Health Information (PHI).

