## 8.2 Exclusion

A subject will be excluded from participating in the study if **any** of the following conditions apply:

1. Known or suspected pregnancy; or at risk for pregnancy from unprotected intercourse earlier in current cycle;
2. Subject who anticipates separation from her partner for more than 1 cycle within the next 12 months;
3. A previously inserted IUD that has not been removed by the time LevoCept is placed;
4. History of previous IUD complications, such as perforation, expulsion, infection (pelvic inflammatory disease) or pregnancy with IUD in place.
5. Injection of any hormonal contraceptive (e.g., Depo-Provera) within the last 10 months;
  - 5.1 Must have had 2 normal menstrual cycles since the last injection;
6. Planned use of any non-contraceptive estrogen, progesterone or testosterone any time during the 12 months of study participation;
7. Postpartum, prior to a minimum of 6 weeks and complete uterine involution;
8. Exclusively breastfeeding before return of menses; Lactating women will be excluded unless they have had at least two normal menstrual periods prior to enrollment.
  - 8.1 Must have had 2 normal spontaneous menstrual cycles since delivery;
9. Unexplained abnormal uterine bleeding (suspicious for serious condition), before evaluation; Immediately post-septic abortion or puerperal sepsis (must wait a minimum of 3 months);
10. Severely heavy or painful menstrual bleeding;
11. Suspected or known cervical, uterine or ovarian cancer, or unresolved clinically significant abnormal pap smear requiring evaluation or treatment.
12. Any history of gestational trophoblastic disease with or without detectable elevated  $\beta$ -hCG levels, or related malignant disease without an intervening normal pregnancy;
13. Any congenital or acquired uterine anomaly that may complicate IUD placement, such as:
  - 13.1 Submucosal uterine leiomyoma
  - 13.2 Asherman's syndrome
  - 13.3 Pedunculated polyps
  - 13.4 Bicornuate uterus
  - 13.5 Didelphus or uterine septa
14. Any distortions (e.g. fibroids), in the opinion of the investigator, likely to cause issues during insertion, retention or removal of the IUD;

15. Known anatomical abnormalities of the cervix such as severe cervical stenosis, prior trachelectomy or extensive conization that, in the opinion of the investigator would prevent cervical dilation and study device placement;
16. Current or recent (within the last 3 months) untreated acute cervicitis or vaginitis;

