## **10. ENROLLMENT**

A subject is considered enrolled into the study after signing the informed consent, PHI and Bill of Rights forms (if applicable) and being found eligible based on her history, physical examination, screening tests and LevoCept insertion attempt. If an eligible consented patient withdraws consent before insertion for any reason this would be considered a screen failure. Enrollment is planned at approximately 250 subjects in a five-month period.

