5.5 Evaluable for Pregnancy Analysis Population

Evaluable for pregnancy (EP) analysis population will include only those safety subjects who underwent the study device placement successfully, and must meet requirements 1, 2 and 3 as follows. Subjects must also meet either requirement 4 or 5 to be EP.

The requirements are

1. between 18 to 35 years of age (inclusive) at enrolment;
2. at least one report of pregnancy status after being enrolled;
3. do not have pre-treatment pregnancy, which is defined as the estimated conception date being before the insertion date.

AND

4. have at least 1 cycle with intercourse and without any backup contraception or emergency contraception;

OR

5. became pregnant while study device LevoCept was in place.

Certain protocol deviations (PDs) are major in which they may affect the ability to assess the true effect of the trial device. Major protocol violations will be those reasonably considered to have had a material impact on the primary efficacy assessment. Subjects with major protocol violations will be excluded from EP analysis population.

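### Section 16 of the protocol allows violations to be approved in advance without exempting the entry criteria, which the rest of the protocol treats as fixed

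*Protocol*

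**What the plan says.** **Advance approval.** Protocol Section 16 opens by requiring the sponsor's written approval for any change to the protocol, except in an emergency or to protect the subject. It then adds: "A protocol violation or deviation may be requested in advance of implementation and will be reviewed for approval by ContraMed or its designee". The same sentence goes on to allow for violations found afterwards. IRB reporting is mentioned for one class only: "Violations or deviations from the Clinical Investigational Plan to protect the health and safety of the subject will be reported to the IRB". All violations and deviations are recorded and tracked "according to process established prior to first patient enrolled"; that process is not described.

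**Entry criteria.** Section 8.1: "Subject must meet all of the following criteria to participate in this study". Section 8.2: "A subject will be excluded from participating in the study if" any listed condition applies. Section 10 counts a woman as enrolled after consent and after "being found eligible based on her history, physical examination, screening tests and LevoCept insertion attempt". Section 12.2 has the entry criteria confirmed again before placement. Section 6.3 puts first among its risk controls: "Establishing eligibility criteria that exclude subjects who are at higher risk for experiencing an anticipated adverse event".

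**Analysis.** SAP Section 5 has the sponsor and its designee approve the analysis populations, with excluded cases and reasons documented. SAP 5.5 adds: "Subjects with major protocol violations will be excluded from EP analysis population". What makes a violation major is left to judgement, without a list.

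**The concern.** A criterion that can be set aside on request is not a fixed criterion. Section 16 places no limit on what may be requested, so read literally it reaches the safety exclusions (uterine anomaly, infection, device allergy) as well as the criteria that make a woman at risk of pregnancy (for example, a partner without a vasectomy).

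Two things would be at stake if the route were used for eligibility. First, a woman could receive a device despite a condition that Section 6.3 counts on screening out. Second, she would either add cycles to the Pearl Index without belonging to the intended population, or be taken out later under the open major-violation test. The trial is open-label and single-arm, and SAP Sections 5 and 5.5 do not require that decision to be made without knowledge of pregnancy.

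**Working it through.** **Step 1: the passages side by side.**

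| Place | Can an entry criterion be set aside? |
|---|---|
| Protocol 8.1, 8.2 | No: all inclusion criteria, no exclusion criterion |
| Protocol 10, 12.2 | No: eligibility needed for enrolment, rechecked before placement |
| Protocol 6.3 | Criteria relied on as a risk control |
| Protocol 16 | Any violation may be requested in advance; no exemption stated |

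Section 16 never mentions eligibility, so it neither permits nor forbids such a waiver. The protocol does not say which passage prevails.

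**Step 2: the plan's own figures.** The inputs are from the protocol's Sample Size section: 225 women aged 18-35, 10 cycles each, 1% without diary data, 9.2% of cycles not evaluable, and 1 pregnancy.

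- Cycles: 225 × 0.99 × 10 × (1 − 0.092) = 2,022.6, close to the stated 2,015.
- Pearl Index: 1 × 1300 / 2,015 = 0.645, stated as 0.6.
- The stated 95% interval (0.1, 3.3) does not come back from 1 event in 2,015 cycles. Exact Poisson gives 0.02 to 3.59. A Poisson score interval on the all-age goal of 2,240 cycles gives 0.10 to 3.29. That match is numerical only, and it is a separate matter from this point. I use exact Poisson below as my own choice.

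**Step 3: dilution if waived women stay in the analysis.** Cycles per woman = 2,015 / 225 = 8.96. Suppose *k* of the women behind the 2,015 cycles were not truly at risk. Then the Pearl Index on properly at-risk cycles is 1300 / (2,015 − 8.96*k*). The documents give no basis for any *k*, so the values are assumptions.

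| *k* (assumed) | Share of cycles | At-risk cycles | Pearl Index (95% CI) |
|---|---|---|---|
| 0 | 0 | 2,015 | 0.65 (0.02, 3.59) |
| 1 | 0.4% | 2,006 | 0.65 (0.02, 3.61) |
| 5 | 2.2% | 1,970 | 0.66 (0.02, 3.68) |
| 10 | 4.4% | 1,925 | 0.68 (0.02, 3.76) |

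**Step 4: removal as a major violator.** If the single planned pregnancy occurred in a woman later classed as a major violator, the result is 0 pregnancies in 2,006 cycles. The Pearl Index becomes 0.00, and the upper limit is 3.689 × 1300 / 2,006 = 2.39, against 3.59 before.

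**Step 5: whether the output would show it.** SAP 6.2.1 lists women who violated entry criteria, and Listing 16.2.2.1 shows which criterion. Listing 16.2.2.2 shows category, reason, classification and the populations affected, but has no dedicated field for advance approval. The only efficacy tables in the SAP index (14.2.1 and 14.2.2) use the EP population.

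**The case against.** The strongest reply is that the specific text governs the general. Section 16 speaks of review for approval, not automatic consent, and the eligibility sections are explicit. The advance-request sentence also fits the section's own opening rule, under which non-emergency changes already need sponsor approval. This stands, and it limits the point to a conflict that needs resolving.

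The exposure argument is also partly answered. Protocol 20.6 and SAP 4.1 drop cycles with no intercourse or with back-up or emergency contraception unless conception occurs, so a woman separated from her partner adds nothing while she is not having intercourse. Irregular cycles do not in themselves make time unexposed. The main remaining route is a woman whose partner has had a vasectomy, and possibly one with a recent contraceptive injection.

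Record-keeping is good: Protocol 19.3 puts every deviation on the eCRF, with full monitoring of women who undergo placement.

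Three stronger readings are tempting and should not be drawn:

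- **That ineligible women are enrolled by waiver.** Nothing documents one, and Sections 8.1, 8.2, 10 and 12.2 read against it.
- **That the IRB is bypassed.** Section 16 is silent on this route, but Section 7 monitors compliance with IRB requirements, Section 19.1 checks that the IRB is notified of approved plan changes as required, and Appendix 1 binds investigators to IRB conditions. Whether these reach a deviation for one subject is unclear.
- **That one company both grants the waiver and judges it.** The sponsor role is common to both steps, but the protocol names ContraMed and the SAP names Sebela, and the link is not explained.

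**Conclusion.** The point holds as a conflict between passages: Section 16 does not rule out advance waivers of entry criteria that the rest of the protocol presents as fixed. The safety consequence cannot be sized from the documents. The effect on the Pearl Index is small, about 0.4% of cycles per woman. Even ten women, an assumed number, move it only from 0.65 to 0.68, well inside an interval of 0.02 to 3.59.

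The larger sensitivity lies downstream. At the planning case of one pregnancy, one major-violation decision moves the estimate from 0.65 to 0 and the upper limit from 3.59 to 2.39. That comes from the open test in SAP 5.5 and would exist without any waiver; barring waivers alone would not cure it. These figures assume the planned event count, an average of 8.96 cycles per woman, and exact Poisson limits.

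**What to change.** 1. **Protocol Section 16.** Keep the advance-request sentence, including its clause on violations found afterwards. Add that the inclusion and exclusion criteria of Sections 8.1 and 8.2 may not be waived by this route, and state what IRB reporting applies to any deviation still approved in advance.
2. **Placement timing and contraception.** Reconcile Section 16 with Section 4.1 and the contraception passages, so that a site can tell whether advance approval applies to them. What those rules should be is a clinical matter and is not proposed here.
3. **SAP Listing 16.2.2.2.** Add a column showing whether each deviation was pre-approved.
4. **SAP Table 14.2.1.** Add a supportive Pearl Index that keeps women who meet every other EP requirement but were removed as major violators. A reader then sees the result with and without that judgement.

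The cost is a slight loss of enrolment flexibility, a short protocol clarification, one listing column and one table row. Enrolment was planned to take about five months and the SAP is dated July 2018, so the protocol change may come too late to affect entry; items 3 and 4 would still be useful.
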